## **1. INTRODUCTION**

This statistical analysis plan (SAP) contains the detailed technical specifications for the data analysis described in the OPP-100 protocol Amendment #2 (13 July 2019).

The reviewer can refer to the study protocol, and the case report form (CRF) for details of study design, conduct and data collection. Specifications of tables, figures, and data listings are contained in a separate document.

If the analyses described in the protocols differ from those in this SAP, the methods of the SAP prevail.

## **2. STUDY OBJECTIVES**

### **2.1 PRIMARY OBJECTIVE(S)**

To assess the relative bioavailability of varenicline administered intranasally at its highest intended clinical strength compared to varenicline administered orally at its highest oral tablet strength.

### **2.2 SECONDARY OBJECTIVE(S)**

To assess the clinical and laboratory safety of varenicline administered as a single dose orally and intranasally.

## **3. STUDY DESIGN**

### **3.1 OVERVIEW**

Protocol OPP-100 is a Phase 1, open-label, randomized, 2-way crossover study to evaluate the relative bioavailability of OC-01 (varenicline) Nasal Spray compared to varenicline administered orally as Chantix®. Approximately 22 healthy volunteer subjects between 18-65 years of age meeting all other study eligibility criteria will be randomized (Treatment Period 1) to receive an intranasal dose of 0.12 mg OC-01 (50 µL spray of 0.06 mg into each nostril) or a single 1 mg oral dose of Chantix®. Both administrations will be delivered while the subject is in an overnight fasted state. Subjects then will return at least 14 days later (Treatment Period 2) to receive the alternate dose of varenicline that was delivered at Treatment Period 1. Again, this delivery will be performed while the subject is in an overnight fasted state.

Participants who terminate early during the application period will be asked to complete safety assessments (if the participants agree) prior to study exit. Participants who are terminated early from the study will not be replaced.

**Table 1: Schedule of Visits and Measurements**

Procedure	Screening	Period 1 Check-In	Period 1	Period 2 Check-In	Period 2	End of Study/Early Termination
	Day -28 to -2	Day -1	Days 1-6	Day 14	Days 15-20	Day 27 + 7 Days
Informed consent/HIPAA	X					
Demographics	X					
Medical history	X					
Eligibility criteria	X					
Urine pregnancy test 	X					X
Serum pregnancy test 		X		X		
Drug and Alcohol Screen	X	X		X		
Physical Examination 	X					X
12-lead ECG	X					X
Vital Signs 	X		X		X	X
Laboratory Samples (hematology, chemistry) 	X		X 		X 	X
Urinalysis	X					X
Intranasal Examination	X	X		X		X
PK Sample Collection 			X		X	
Randomization			X			
Administer OC-01 (varenicline) Nasal Spray/Chantix®			X		X	
Concomitant medications	X	X	X	X	X	X
AE Query			X	X	X	X

 For females of childbearing potential  
Weight and height collected at Screening Visit only  
Vital signs including heart rate, respiratory rate and blood pressure will be obtained at Screening, prior to treatment administration at Periods 1 and 2, and 2 hours post treatment administration at Periods 1 and 2, and End of Study/Early Termination.  
Clinical Chemistry to be performed at Screening, and 2 hours post treatment administration Periods 1 and 2, and End of Study/Early Termination. Hematology to be performed at Screening and End of Study/Early Termination.  
PK samples collected at the following timepoints (predose, 5 minutes, 15 minutes, 30 minutes, 1 hour, 2 hours, 3 hours, 4 hours, 6 hours, 8 hours, 12 hours, 24 hours, 36 hours, 48 hours, 72 hours, 96 hours, 120 hours). Samples collected up to and including 48 hours will be performed In-Unit. Following the 48 hours sample collection subjects will be discharged and return for remaining samples on an Out-Patient basis.

### 3.2 STUDY POPULATION

All subjects must be between 18-65 years of age, inclusive of either gender, and of any race, and must meet all inclusion criteria and none of the exclusion criteria.

### 3.3 SAMPLE SIZE AND POWER CONSIDERATIONS

This study is designed to test the relative bioavailability of 2 treatments (single oral dose of 1 mg varenicline [Chantix®] and Intranasal dose of 0.12 mg varenicline [OC-01]).

[REDACTED]

**Table 2: Interim Analysis Matrix**

[REDACTED]	[REDACTED]
[REDACTED]	[REDACTED]
[REDACTED]	[REDACTED]
[REDACTED]	[REDACTED]
[REDACTED]	[REDACTED]

### 3.4 RANDOMIZATION

Subjects will be randomized in a 1:1 ratio to receive treatment sequence 1 or 2. Treatment sequence 1 is treatment A: Single oral dose of 1 mg varenicline (Chantix®) administered orally in Period 1 and treatment B: Intranasal dose of 0.12 mg OC-01 (varenicline)- delivered as a 50 µL (0.06 mg) spray into each nostril in Period 2. Treatment sequence 2 is treatment B: Intranasal dose of 0.12 mg OC-01 (varenicline)- delivered as a 50 µL (0.06 mg) spray into each nostril in Period 1 and treatment A: Single

oral dose of 1 mg varenicline (Chantix®) administered orally in Period 2. This study will be open-label and no blinding procedures will be necessary.

## 4. ANALYSIS SETS

### 4.1 PHARMACOKINETICS ANALYSIS SET

[REDACTED]

### 4.2 SAFETY ANALYSIS SET

[REDACTED]

## 5. ENDPOINTS

### 5.1 PHARMACOKINETICS ENDPOINTS

The follow pharmacokinetic parameters will be calculated on the varenicline plasma levels:

- [REDACTED]

### 5.2 SAFETY ENDPOINTS

- [REDACTED]

## 6. GENERAL CONSIDERATIONS FOR STATISTICAL ANALYSIS

All statistical analyses and data summaries will be performed using SAS® (version 9.4). Tables and listings will be prepared in accordance with the current ICH Guidelines. [1]

[2] In general, data will be summarized using descriptive statistics.

[REDACTED]

[REDACTED]

[REDACTED]

[REDACTED]

### 6.1 STUDY DAY

Study day is calculated as assessment date minus date of first dose of study drug + 1 if the assessment occurred after the date of first dose of study drug. For assessments that occurred before the first dose of study drug, study day is calculated as assessment date minus date of first dose of study drug. Date of first dose is defined as study Day 1.

## 6.2 BASELINE

Unless otherwise specified, the baseline value is defined as the last assessment prior to administration of the first dose.

## 7. PATIENT DISPOSITION

The number of subjects who complete the study, and who discontinue the study will be tabulated for the Safety Analysis Set by treatment sequence.

## 8. PROTOCOL DEVIATION

Major protocol deviations will be summarized by treatment sequence for Safety Analysis Set.

## 9. DEMOGRAPHICS AND BASELINE CHARACTERISTICS

Demographic and other baseline characteristics for the Safety Analysis Set and Pharmacokinetic Analysis Set will be summarized using descriptive statistics by treatment sequence.

Continuous demographic and baseline variables include age, BMI, weight, and height; categorical variables include gender, ethnicity, and race.

## 10. MEDICAL HISTORY

Medical history (recorded at the screening visit) will be coded using the Medical Dictionary for Regulatory Activities (MedDRA) version 22.0 and will be summarized by system organ class (SOC) and preferred term (PT). The summary will be presented by treatment sequence for the Safety Analysis Set.

## 11. PRIOR AND CONCOMITANT MEDICATION

[REDACTED]

[REDACTED]

[REDACTED]

[REDACTED]

[REDACTED]

[REDACTED]

- [REDACTED]

[REDACTED]

## 12. PHARMACOKINETIC ANALYSES

### 12.1 GENERAL CONSIDERATIONS

Pharmacokinetics parameters will be calculated by NCA (Non-compartmental analysis) and evaluated for the PK analysis set.

[REDACTED]

[REDACTED]

[REDACTED]

### 12.2 PRIMARY ANALYSIS

[REDACTED]

[REDACTED]

### 12.3 PK CONCENTRATION

[REDACTED]

[REDACTED]

### 12.4 PK PARAMETERS

[REDACTED]

[REDACTED]

### 12.5 HANDLING OF MISSING VALUES AND OUTLIERS

[REDACTED]

## 13. SAFETY ANALYSIS

### 13.1 EXTENT OF EXPOSURE

Dose and time of dosing will be listed per subject. The number of subjects who received each treatment will be summarized by treatment sequence.

### 13.2 ADVERSE EVENTS

Adverse events (AEs) will be coded using the Medical Dictionary for Regulatory Activities (MedDRA) version 22.0.

A treatment-emergent AE is any AE occurring after the administration of the study drug and within 5 days after study drug administration, or a pre-treatment AE or pre-existing medical condition that worsens in intensity after start of the study drug and within the time of residual drug effect in both periods.

All AE data will be listed by subject. Only treatment-emergent AEs will be presented in summary tables by treatment.

For treatment emergent AEs overview summary table, by treatment and overall, will be prepared and including number of subjects reporting an AE, the percentage of subjects (%) with an AE and the following categories:

- Any Treatment-emergent adverse events (TEAEs)
- Deaths
- Serious TEAEs
- Study drug related TEAEs
- TEAEs leading to withdrawal
- TEAEs leading to death

Summaries of the following TEAEs will be provided by system organ class (SOC) and preferred term (PT):

- All TEAEs
- Study drug related TEAEs
- Serious adverse events (SAEs)
- TEAEs by severity

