#### 8.10. Monitoring and Quality Assurance

# 9. SAFETY DEFINITIONS, SAFETY MONITORING AND REPORTING

#### 9.1. Adverse Event

An adverse event (AE) is defined as any untoward medical occurrence associated with the use of a drug in humans, whether or not the event is considered drug-related. An AE can therefore be any unfavorable and unintended sign (e.g., an abnormal laboratory finding), symptom, or disease occurring after the subject started dosing with the study drug, without any judgment about causality. Any pre-existing medical condition that worsens after administration of the study drug will also be considered a new AE.

Study drug includes the investigational drug under evaluation. Documentation regarding the AE should be made as to the nature, date of onset, end date, severity, expectedness relationship to study drug, action(s) taken, seriousness, and outcome of any sign or symptom observed by the Investigator or reported by the subject upon indirect questioning. AE collection will start following the first administration of study drug until the last follow up visit of the study.

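### SAP 13.2 tabulates new AEs by treatment only when they start within 5 days of a dose; later new AEs are listed but enter no by-treatment table named there

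*SAP*

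**What the plan says.** SAP 13.2 defines the event to be tabulated: "A treatment-emergent AE is any AE occurring after the administration of the study drug and within 5 days after study drug administration". A second limb admits earlier events or existing conditions that worsen after dosing, provided this happens "within the time of residual drug effect in both periods"; the readable text gives that time no length. Two output rules follow: "All AE data will be listed by subject", and "Only treatment-emergent AEs will be presented in summary tables by treatment". The two table sets then named, the overview and the SOC/PT summaries, are both introduced as tables of treatment-emergent events.

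Collection runs longer than the window. Protocol 9.1 says: "AE collection will start following the first administration of study drug until the last follow up visit of the study". Protocol 9.2 starts SAE collection at consent and ends it at the same visit. Protocol Section 2 and SAP 2.2 make clinical and laboratory safety of the oral and intranasal doses the secondary objective.

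**The concern.** The by-treatment tables are where a reader compares the two routes. A new AE that starts 8 days after a dose is collected and listed, yet it is not treatment-emergent under 13.2 and so is absent from those tables. The same applies to a nasal AE whose recorded onset is the Day 14 check-in or the End of Study examination. At stake is whether the by-route AE counts reflect the follow-up that the trial pays for, including the visits at which the nasal mucosa is actually examined.

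**Working it through.** The documents' only figure on this point is the 5-day window. It equals the time of the last PK sample in Protocol 8.4 (120 h / 24 = 5 days), although the SAP does not give that as its reason.

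**Inputs.** First dose Day 1 (SAP 6.1). Second dose Day 15, which is the minimum 14-day separation (Protocol 8.3.1). End of Study is Day 27 + 7, so Days 27-34, in Protocol 8.3.1 and Appendix 1. The Synopsis puts it 7-14 days after the final dose, so Days 22-29. The two timings need reconciling in their own right; both are carried here.

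**Step 1: days outside the windows.** Counting the dose day plus 5, the windows are Days 1-6 and Days 15-20, 12 calendar days. New AEs on Days 7-14, and from Day 21 to End of Study, fall outside.

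**Step 2: share of follow-up outside.** The SAP does not say whether 5 days means calendar days or 120 hours, so both are shown. With End of Study on Day E, the calendar share is (E - 12)/E. The elapsed share is (E - 1 - 10)/(E - 1).

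| End of Study | Calendar days | Elapsed time |
|---|---|---|
| Day 22 | 10/22 = 45.5% | 11/21 = 52.4% |
| Day 27 | 15/27 = 55.6% | 16/26 = 61.5% |
| Day 29 | 17/29 = 58.6% | 18/28 = 64.3% |
| Day 34 | 22/34 = 64.7% | 23/33 = 69.7% |

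**Step 3: scheduled post-dose assessments in completers (Appendix 1).**
- Intranasal examination: Day 14, which is 13 days after dose 1, and End of Study, which is 27 - 15 = 12 to 34 - 15 = 19 days after dose 2 (7-14 on the Synopsis timing). All exceed 5.
- Physical examination, ECG, hematology, urinalysis: End of Study only. All are outside.
- Vital signs and chemistry at 2 hours: inside.

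**Step 4: where late findings do go.** Hematology and chemistry have post-baseline shift tables (SAP 13.3), and urinalysis has a baseline-to-end shift table (13.4). ECGs are summarised over all subjects (13.7). Significant physical findings go to the medical history and AE listings (13.8). Abnormal intranasal results are listed only (13.9).

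**Step 5: follow-up by route if all post-dose AEs were tabulated by most recent treatment.** Period 1 gives 14 days; Period 2 gives 12 (End of Study Day 27) to 19 (Day 34).
- 11 subjects per sequence, all complete: 11×14 + 11×12 = 286 to 11×14 + 11×19 = 363 subject-days, the same for each route.
- Four of 22 leave the oral-first sequence at the end of Period 1. Oral: 286/22 = 13.0 to 363/22 = 16.5 days per dosed subject. Nasal: (11×14 + 7×12)/18 = 13.2 to (11×14 + 7×19)/18 = 15.9. The gap is at most about 0.6 day.
- The same four leave at Day 6 (5 days each). Oral: (7×14 + 4×5 + 11×12)/22 = 11.4 to (7×14 + 4×5 + 11×19)/22 = 14.9. Nasal is unchanged. The gap is about 1.9 to 1.1 days.
- The Day 6 case on the Synopsis timing (Period 2 of 7 to 14 days). Oral: (98 + 20 + 77)/22 = 8.9 to (98 + 20 + 154)/22 = 12.4. Nasal: (154 + 49)/18 = 11.3 to (154 + 98)/18 = 14.0. The gap is about 2.4 to 1.6 days.

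**The case against.** The best case for the plan is that nothing here is an error. A short window is a sound way to attribute events in a crossover, it treats both routes alike, and with about 22 subjects a complete listing lets anyone see each late event. The restricting sentence governs tables by treatment and leaves room for an overall or by-sequence table. Protocol 10.4.2.1 shows no text, SAP 5.2 and much of SAP 6 are redacted, and SAP 1 places table specifications in a separate document. An event found at a late visit may carry an earlier onset, and an early-termination visit can fall inside the window. Protocol 9.1 already treats worsening of an existing condition as a new AE.

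Most of this stands, and it keeps the point minor. It does not remove the fact that no by-treatment table named in 13.2 takes a late-onset new AE.

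Three stronger readings are tempting, and the documents do not support them:
- *The SAP contradicts the protocol.* It does not. Collecting over a longer period than one tabulates is consistent.
- *Late AEs are lost.* They are listed by subject.
- *Late SAEs and deaths are certainly left out of the tables.* For SAEs the text does lean to the 5-day limit: the restricting sentence, the overview row "Serious TEAEs" and the heading over the SOC/PT list all point that way, and only the SAE bullet's own label lacks the qualifier. For deaths the overview has an unqualified row beside a separate row for fatal treatment-emergent events, so its natural reading is all deaths. Neither scope is stated outright.

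**Conclusion.** The point holds as a minor gap in tabulation. New AEs with onset on about Days 7-14 or after about Day 20 are listed but enter no by-treatment table named in SAP 13.2. The part outside the windows is 45%-65% of post-dose follow-up by calendar days, or 52%-70% by elapsed time. This does not estimate the share of AEs affected, which cannot be computed from the documents and is probably smaller. The practical weight comes from the schedule: for completers, all post-dose intranasal examinations come after the window, and SAP 13.9 only lists their abnormal results.

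The conclusion assumes dosing exactly 14 days apart, recorded onset as the date that decides, no event admitted through the worsening limb, and no extra table in redacted text or the separate specifications. The undefined residual-effect time is a matter of wording and adds nothing to the size of the point.

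**What to change.** In SAP 13.2:
1. Keep the 5-day tables and label them as the attribution analysis.
2. Add one SOC/PT table of all AEs with onset or worsening from first dose to End of Study, assigned to the most recently administered treatment, with a note on follow-up length by period.
3. State that SAEs and deaths are counted over that same whole post-dose period; show any SAE between consent and first dose separately.
4. As a clarification only, say what the residual-effect time is and whether 5 days means 120 hours or calendar days.

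If the table specifications already contain such a table, a cross-reference in 13.2 is enough.

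The cost is some SAP wording and one table from data already collected. A few late, possibly unrelated events would enter the added table. Follow-up per dosed subject could also differ by route: not at all if all complete with 11 per sequence, but by about 2 days if four subjects leave one sequence early in Period 1.

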### **13.3 LABORATORY EVALUATIONS**

Hematology and chemistry laboratory results will be classified as low (L), normal (N), or high (H) according to the laboratory-supplied reference range. Shift tables will be presented for each laboratory test for post-baseline assessments.

### **13.4 URINALYSIS**

Urinalysis results will be listed by subject. Urinalysis results will be classified as normal or abnormal according to the laboratory-supplied reference range. Shift table from baseline to end of study will be presented for each laboratory test.

### **13.5 PREGNANCIES**

Pregnancy test results will be presented in by-patient listing for further medical review.

### **13.6 VITAL SIGNS**

Period baseline for all vital sign analyses will be the last assessment prior to the period study drug administration.

For each period, change from period baseline, will be derived for 2 hours post treatment. These changes from baseline values will also be summarized descriptively for each assessment time by treatment.

### **13.7 ECG**

ECGs results will be listed by subject and summarized descriptively by overall subjects.

### **13.8 PHYSICAL EXAMINATION**

Significant findings for physical examination will be collected as medical history and adverse events. They will be reported in the listings of medical history and adverse events.

### **13.9 INTRANASAL EXAMINATION**

Intranasal examinations abnormal results will be listed by subject.

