#### End of Study/Early Termination (Day 27 + 7):

- Urine pregnancy test (if applicable)
- Physical Examination
- 12-lead ECG
- Vital Signs
- Laboratory Samples (hematology, chemistry)
- Urinalysis
- Intranasal Examination
- Concomitant Medications
- AE Query

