#### 8.5.2. Unscheduled Visits

These visits may be performed in order to ensure subject safety. All procedures performed at an unscheduled visit will be recorded in the source.

Evaluations that may be conducted at an Unscheduled Visit include:

- Intranasal Examination
- Physical Examination
- Vital Signs
- 12 lead ECG
- Laboratory assessments/urinalysis
- Urine pregnancy test (if applicable)
- Assessment of AEs
- Assessment of concomitant medications and/or treatments
- Any other assessments needed in the judgment of the investigator

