#### A1. Intranasal Examination

Qualified participants for the study must undergo an intranasal exam to make the final eligibility determination (e.g. severe nasal airway obstruction such as, severe septal deviation or inferior turbinate hypertrophy, or vascularized polyp seen on examination are reasons for exclusion). To monitor nasal mucosal integrity during the study for participant safety, an examination of the nasal cavities via an intranasal exam will be performed at the Screening Visit (after all other screening procedures have been completed), Periods 1 and 2 Check-in, and at the End of Study/Early Termination Visit. This examination will be performed by an Ear Nose and Throat (ENT) specialist, otolaryngologist or other suitably qualified medical practitioner (i.e. one who has been trained to perform intranasal exam). The procedure used for the intranasal exam can be conducted either by endoscopic examination or nasal specula.

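### Does listing intranasal findings by subject, with no by-treatment table, leave nasal safety unreported because the scheduled post-dose exams fall outside the 5-day TEAE window?

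*SAP*

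**What the plan says.** Four parts of the plan bear on this.

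- **Reporting of the exam.** SAP 13.9 consists of one sentence: "Intranasal examinations abnormal results will be listed by subject". The visible text has no count, shift table or summary by treatment.
- **Adverse event tables.** SAP 13.2 defines the term thus: "A treatment-emergent AE is any AE occurring after the administration of the study drug and within 5 days after study drug administration". A second limb admits a pre-treatment event or existing condition that "worsens in intensity after start of the study drug and within the time of residual drug effect in both periods"; the visible text gives that time no length. SAP 13.2 adds: "Only treatment-emergent AEs will be presented in summary tables by treatment". The same section lists all adverse events by subject, treatment-emergent or not.
- **Purpose and timing of the exam.** Protocol Appendix 2, A1 gives the purpose as "To monitor nasal mucosal integrity during the study for participant safety". After Screening, the exam is scheduled at "Periods 1 and 2 Check-in, and at the End of Study/Early Termination Visit". Protocol 8.5.2 also allows it at unscheduled visits.
- **Status of the analysis.** Protocol sections 3 and 10.3 state that no hypothesis is tested. SAP section 1 places the table and listing specifications in a separate document. SAP 5.2 and parts of SAP 6 are redacted, and protocol 10.4.2.1 shows no text.

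**The concern.** Safety of both routes is the secondary objective, and the intranasal exam is the assessment closest to the site of the test product. Two features together look like a gap. The by-treatment tables take new events only from a short window after each dose, and the scheduled post-dose exams all come later. A new nasal finding whose onset is dated to the exam would therefore appear in a listing and in no by-treatment table.

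The contrast with other sections adds to the impression. SAP 13.4 gives urinalysis a normal/abnormal shift table, although its only scheduled post-baseline value in a completer follows both treatments. The intranasal exam has a pre-dose and post-dose pair around each dose, and receives a listing only. If this were a real loss, a lasting mucosal change after the spray could go uncounted.

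**Working it through.** **Inputs.** First dose on Day 1 (SAP 6.1). Period 2 check-in on Day 14 and second dose on Day 15 (protocol 8.3.1). End of Study on Day 27 to 34 (protocol 8.3.1, Appendix 1), or 7 to 14 days after the final dose (protocol synopsis). Window of 5 days (SAP 13.2). About 22 enrolled, and about 18 completing the PK assessments (protocol synopsis).

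**Step 1: do the exams miss the window?** The windows are Day 1 to 1 + 5 = 6, and Day 15 to 15 + 5 = 20.

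| Scheduled exam | Days after last dose | Days past window |
|---|---|---|
| Period 2 check-in, Day 14 | 14 − 1 = 13 | 13 − 5 = 8 |
| End of Study, Day 27 | 27 − 15 = 12 | 12 − 5 = 7 |
| End of Study, Day 34 | 34 − 15 = 19 | 19 − 5 = 14 |
| Synopsis timing, earliest | 7 | 7 − 5 = 2 |
| Synopsis timing, latest | 14 | 14 − 5 = 9 |

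They do, in every completer and on either End of Study timing. A gap between periods longer than 14 days moves the first exam later still. The premise is correct.

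**Step 2: what does missing the window cost?**

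- A reaction with onset in the first 5 days is treatment-emergent whenever it is detected. Adverse event queries run in Periods 1 and 2 (Days 1–6 and 15–20), so symptomatic nasal reactions are asked about inside the windows.
- An early-termination or unscheduled exam can itself fall inside a window.
- What remains is a new finding, in practice mostly one without symptoms, with onset dated to the exam. It is listed under SAP 13.9. If recorded as an adverse event, which the definition in protocol 9.1 allows for any unfavorable sign after dosing, it is listed again under SAP 13.2.

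No abnormal result disappears.

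**Step 3: can the listing be read by treatment?** There are two scheduled post-dose exams per subject, so at most 22 × 2 = 44 results (18 × 2 = 36 if 18 are examined). SAP 13.1 lists dose and time of dosing per subject, and SAP 6.1 assigns assessments a study day. Given the exam date or visit in the listing (an assumption, since listing layouts are in the separate document), each abnormal result can be placed after the oral or the nasal dose and compared with that subject's earlier exams.

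**Step 4: what would a table add?** The exact two-sided 95% upper limit for 0 findings in n subjects is 1 − 0.025^(1/n).

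| Group (n assumed) | n | Upper limit |
|---|---|---|
| Nasal dose, both sequences | 22 | 15.4% |
| Nasal dose, both sequences | 18 | 18.5% |
| Oral dose, oral-first sequence only | 22/2 = 11 | 28.5% |
| Oral dose, oral-first sequence only | 18/2 = 9 | 33.6% |

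The oral rows use one sequence because only there is the oral exam pair free of an earlier nasal dose; they assume equal loss per sequence. These limits depend on n alone. They are the same whether the results are listed or tabulated.

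**The case for a change.** The best case for a change has four parts.

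- **Only abnormal results are listed.** The number examined and a return to normal are not shown directly. This stands in part. Completion by sequence (SAP 7) and the number receiving each treatment (SAP 13.1) approximate the denominator in completers, and a finding listed at one attended exam and absent at the next can be taken as resolved. A missed exam would not be visible from this listing alone.
- **SAP 13.8 routes significant physical findings to medical history and adverse events; SAP 13.9 has no such sentence.** True, but the definition in protocol 9.1 does not depend on it, and the abnormal result is listed in any case. SAP 13.8 also reports the other clinician-performed examination through listings only, so SAP 13.9 is in line with its nearest neighbour.
- **Urinalysis gets a shift table.** True, but it runs from baseline to end of study and is not described as by treatment. ECG is summarized over all subjects (SAP 13.7). Neither is a precedent for a by-treatment display.
- **A table is cheap.** Less so than it seems. In the nasal-first sequence the Day 14 exam, which would be the period baseline for the oral dose, already follows the nasal dose. A simple by-treatment shift could read a persisting or recovering nasal change as an oral result. Avoiding that needs further displays by sequence and against Day −1. The dated listing keeps the order of events visible.

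The two End of Study timings, Day 27 to 34 against 7 to 14 days after the final dose, do not agree and should be reconciled. That is a separate matter; the result here is the same under both.

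**Conclusion.** The concern does not hold. The timing is as described: no scheduled post-dose intranasal exam in a completer falls within 5 days of a dose, the nearest being 2 days outside. But no rule in the plan yields a wrong or missing result. Early-onset reactions reach the by-treatment tables, all abnormal exam results and all adverse events are listed, and the study makes no formal safety comparison that a table would serve. With at most 44 scheduled post-dose exams, the change after each treatment can essentially be read from the listing. A shift table would be sparse, would describe only persisting or late-detected change, and would alter no conclusion.

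This rests on two assumptions: that the listing identifies the exam date or visit, and that the numbers examined lie between the planned 18 and 22. That no table exists cannot be established either, since part of the SAP is redacted and the table specifications are in another document. Listing or tabulating these results is the sponsor's choice of presentation.
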